3.1.3 Open-Label Treatment

For patients with an inadequate treatment response at Week 76, open-label treatment with obinutuzumab will be provided if all of the following criteria are met at Week 76:

- Inadequate treatment response
- Clinically meaningful improvement from baseline in renal parameters or prior clinically meaningful improvement from baseline followed by worsening
- Need for intensification of therapy
- No unmanageable treatment-emergent adverse events
- No rescue therapy (except corticosteroid-only rescue; see Section 4.4.4.1.1) or treatment failure

Documentation of these criteria will be submitted to the Medical Monitor for review. Investigators may discuss the appropriateness of OLT directly with the Medical Monitor if needed. For patients who initiate OLT based on the Week 76 assessment, the first OLT visit (OLT Day 1) will occur on Week 80.

Additionally, patients who, during blinded treatment after Week 80, experience a loss of adequate response requiring intensification of therapy and without unmanageable treatment-emergent adverse events may initiate OLT once 60 days have elapsed from the most recent obinutuzumab or placebo infusion.

During OLT, patients will receive obinutuzumab 1000 mg on OLT Day 1 and OLT Weeks 2, 24, 26, 52, and once every 6 months thereafter. Background immunosuppression, including doses of corticosteroids and MMF, may be adjusted at the investigator's discretion beginning at OLT Day 1.

During OLT, investigators should regularly review the study safety plan (see Section 5.1), including the risks associated with obinutuzumab (see Section 5.1.1) and management of specific adverse events that may be related to obinutuzumab (see Section 5.1.3.3), to ensure the patient has not developed a condition that would warrant discontinuation of obinutuzumab infusions. Prior to resuming OLT after treatment

interruption, investigators should refer to Section 5.1.3.2 to ensure the patient meets the criteria for resuming treatment.

After study unblinding (see Section 3.1.5), no further OLT will be initiated and ongoing OLT will be discontinued after OLT Week 52. Subsequent access to obinutuzumab may occur through post-trial access (see Section 4.3.4).

Patients who discontinue OLT will enter SFU (see Section 3.1.4).

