4.4.4.1.1 Corticosteroid Rescue

Use of high doses of corticosteroids shortly before the primary endpoint at Week 76 may affect this assessment and should be avoided. Administration of any of the following from Week 64 onward will be considered rescue:

- Methylprednisolone ≥ 100 mg IV or equivalent
- Prednisone ≥ 20 mg/day or equivalent (mean dose) over any 2-week period

Patients who receive corticosteroid rescue will be treated as nonresponders. Patients who receive rescue with corticosteroids alone are not required to discontinue obinutuzumab or placebo infusions and may be eligible for OLT if all eligibility criteria are met (see Section 3.1.3).

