4.2.1.1 Intercurrent Events

The intercurrent events include rescue therapy, treatment failure, study treatment discontinuation, death and early study withdrawal.

Rescue therapy: In some cases of worsening or severely active disease, the investigator may conclude that the patient has failed the randomized treatment regimen and requires rescue therapy.

Two categories of rescue therapies will be considered for the study:

Rescue therapy excluding corticosteroids

Rescue therapies in this category include the following:

Cyclophosphamide

- Anti-CD20 antibodies, including rituximab, ocrelizumab, ofatumumab, and obinutuzumab (if given outside the study protocol)
- Calcineurin inhibitors including ciclosporin, tacrolimus, and voclosporin
- Other investigational, biologic, or targeted therapies used for the treatment of SLE or LN

Patients who receive these rescue therapies will discontinue obinutuzumab or placebo infusions. These patients will continue to be followed according to the study schedule of activities through Week 76 and for at least 12 months from the last dose of obinutuzumab or placebo.

Corticosteroid only rescue

Patients who receive high doses of corticosteroids shortly before the primary endpoint at Week 76 will be considered to have received rescue therapy. Administration of any of the following from Week 64 onward will be considered rescue:

- Methylprednisolone ≥100 mg IV or equivalent
- Prednisone ≥20 mg/day or equivalent (mean dose) over any 2-week period

Any IV or IM corticosteroids will be converted to Methylprednisolone equivalent to evaluate the Methylprednisolone \geq 100 mg IV or equivalent criteria. As for evaluating the prednisone \geq 20 mg/day or equivalent criteria, oral, IV, and IM corticosteroids will be converted to prednisone equivalent dose.

Methylprednisolone pre-medication given prior to obinutuzumab/placebo infusion as per protocol will be exempted from corticosteroid rescue criteria.

Patients who receive corticosteroid rescue will be treated as non-responders. Patients who receive rescue with corticosteroids alone are not required to discontinue obinutuzumab or placebo infusions.

This same rule related to corticosteroid rescue received within 12 weeks prior to endpoint evaluation will also be applied to other secondary and exploratory renal response endpoints (where applicable), including CRR, PRR, ORR, and proteinuric response at Weeks 24, 50, 76, and post Week 76 timepoints.

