4.5 SAFETY ANALYSES

The safety analyses will be performed on the safety-evaluable population as defined in Section 3.1.3 with data collected in the Week 76 treatment period for each patient. Safety outputs will include data until the point of rescue for the patients who receive rescue therapy (excluding corticosteroid rescue). Limited key safety outputs will be produced for post-rescue data.

Safety data will be summarized by the obinutuzumab (combined treatment groups) and placebo groups. Additionally, combined obinutuzumab treatment group will be further broken down to obinutuzumab arm 1 (2-2-2 regimen) and obinutuzumab arm 2 (2-2-1 regimen) for selected key safety data up to Week 76.

Additional analysis including post Week 76 data collected till CCOD will be produced. The post Week 76 analysis details are provided in Section 4.6.7.

4.5.1 Extent of Exposure

A summary of exposure to study treatment will be produced using the dose recorded on the electronic Case Report Form (eCRF). The number of blinded obinutuzumab infusions and treatment duration will be summarized. Obinutuzumab treatment duration will be calculated as difference between date of last dose and date of first dose plus one day.

MMF exposure will be summarized using treatment duration and total cumulative dose.

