The analysis will be based on post Week 76 blinded treatment efficacy-evaluable population as defined below.

Post Week 76 blinded treatment efficacy-evaluable population: Post Week 76 blinded treatment efficacy-evaluable population will consist of patients who continue blinded treatment period post Week 76 and reach at the specified endpoint assessment visits by CCOD. Patients enter the blinded treatment period, but later moved to OLT or SFU period or withdraw from the study prior to endpoint assessment, but would otherwise reach to the assessment visit by CCOD will be included. Patients will be grouped according to randomized (assigned) treatment, rather than treatment received. Patients

who received an incorrect therapy will be reported under the treatment group to which they were randomized.

4.6.7 All Exposure Safety Analyses including Post-Week 76 Data

In addition to the safety analyses detailed in Section 4.5, an All Exposure safety analysis will be performed including post Week 76 data from both blinded treatment and Open-Label Treatment (OLT) period.

The obinutuzumab arm of the All Exposure analysis will comprise of safety data from patients that received any dose of obinutuzumab. Patients that receive any dose of obinutuzumab, whether during the blinded treatment period or post Week 76 via OLT, will contribute safety data from their first dose of obinutuzumab until their last dose +6 months, the CCOD, study withdrawal or receipt of rescue therapy (whichever occurs first):

- Patients randomized to obinutuzumab at Day 1 who achieve adequate or inadequate response at the Week 76 primary analysis will continue to receive obinutuzumab (either blinded or open label). These patients will therefore contribute safety data to the obinutuzumab all exposure arm from their first dose at Day 1 following randomization.
- Patients randomized to placebo at Day 1 who achieve inadequate treatment response at Week 76 will switch to open label obinutuzumab treatment. These patients will therefore contribute safety data to the obinutuzumab all exposure arm following their first dose after switching to obinutuzumab treatment in the OLT period of the trial. Patients that switch from placebo to obinutuzumab will also be rebaselined as of their first dose of obinutuzumab during the OLT period.

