The placebo arm of the All Exposure analysis comprises safety data from patients that received any dose of placebo. Patients that received any dose of placebo during the blinded treatment period including post Week 76, will contribute safety data from their first dose of placebo until their last dose+6 months, the CCOD, receipt of obinutuzumab - 1 day or study withdrawal (whichever occurs first):

- Patients randomized to placebo at Day 1 who achieve adequate response at the
 Week 76 primary analysis will continue to receive placebo during continued blinded
 treatment period. These patients will therefore contribute safety data to the placebo
 all exposure arm from their first dose following randomization, until their last placebo
 dose+6 months, the CCOD or study withdrawal (whichever occurs first)
- Patients randomized to placebo at Day 1 who achieve inadequate response at the Week 76 primary analysis will switch to obinutuzumab treatment during OLT period.
 These patients will therefore contribute safety data to the placebo all exposure arm from their first dose following randomization up until they switch to obinutuzumab.

The following will be summarized in the All Exposure safety analysis:

AEs

- SAEs
- AESIs
- Deaths

All exposure safety analysis population: The All exposure safety analysis population is defined as patients who received any part of blinded infusion of obinutuzumab or placebo during blinded treatment or open label treatment period. Patients who were randomized to the study but who did not receive any part of blinded infusion of obinutuzumab or placebo will not be included in the all exposure safety analysis population. Patients will be grouped according to the treatment that patients actually received rather than the treatment assigned.

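### The All Exposure safety analysis (SAP 4.6.7) ends obinutuzumab-arm data at rescue therapy, gives the placebo arm no general rescue cut-off, and omits the corticosteroid exemption of SAP 4.5

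*SAP*

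**What the plan says.** The All Exposure analysis in SAP 4.6.7 tabulates AEs, SAEs, AESIs and deaths from first dose onward, including blinded and open-label (OLT) data after Week 76. Each arm has its own end-date list:

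- Obinutuzumab arm: data count "until their last dose +6 months, the CCOD, study withdrawal or receipt of rescue therapy".
- Placebo arm: data count "until their last dose+6 months, the CCOD, receipt of obinutuzumab - 1 day or study withdrawal (whichever occurs first".
- Placebo patients with an adequate response at Week 76: a separate bullet ends their data at the last placebo "dose+6 months, the CCOD or study withdrawal (whichever occurs first".

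No reason is given for the difference.

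SAP 4.5, the main safety analysis, has a single rule for all patients: "Safety outputs will include data until the point of rescue for the patients who receive rescue therapy (excluding corticosteroid rescue". It then promises limited key outputs on data after rescue. That section is confined to the Week 76 treatment period and sends the reader to 4.6.7 for later data.

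On what counts as rescue, SAP 4.2.1.1 states "Two categories of rescue therapies will be considered for the study": one made up of agents other than corticosteroids, the other corticosteroid-only. For the second, "Administration of any of the following from Week 64 onward will be considered rescue". Under Protocol 4.4.4.1, rescue with the non-corticosteroid agents stops infusions and bars OLT. Under Protocol 4.4.4.1.1, by contrast, "Patients who receive rescue with corticosteroids alone are not required to discontinue obinutuzumab or placebo infusions and may be eligible for OLT" if the other criteria are met. The OLT criteria in Protocol 3.1.3 agree: "No rescue therapy (except corticosteroid-only rescue; see Section 4.4.4.1.1) or treatment failure".

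**The concern.** The two lists are censoring rules that a programmer will apply as written, and they treat the same event differently by arm. A patient on obinutuzumab who receives cyclophosphamide leaves the tables that day. A patient on placebo who receives it stays in for up to 6 months after the last infusion. Patients needing rescue have worsening or severely active disease and then receive further immunosuppression, so this period may well carry serious events. Counting it mainly in one arm makes the columns for SAEs, AESIs and deaths not comparable.

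The missing corticosteroid exemption is a second difficulty. If rescue in the obinutuzumab list takes its meaning from SAP 4.2.1.1, a corticosteroid-only rescue ends the data of a patient who may still be receiving obinutuzumab. An analysis of all exposure is meant to capture that time.

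**Working it through.** The plan states no figure on this point, so there is none to reproduce. The check compares the rules and then works out the windows.

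**1. Effect of each kind of rescue on a patient's data**

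| Event | SAP 4.5, all patients | SAP 4.6.7, obinutuzumab arm | SAP 4.6.7, placebo arm |
|---|---|---|---|
| Obinutuzumab given outside the protocol | ends data | ends data | ends data (day before) |
| Cyclophosphamide, calcineurin inhibitor, other anti-CD20 antibody, other agent | ends data | ends data | does not end data |
| Corticosteroid-only rescue | does not end data | ends data, if read with SAP 4.2.1.1 | does not end data |

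The second row is a stated difference between arms. The third depends on how one unqualified phrase is read.

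**2. Extra placebo time after non-corticosteroid rescue**

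Inputs from the documents: infusions at Weeks 0, 2, 24, 26, 50 and 52; infusions stop at rescue (Protocol 4.4.4.1); AE reporting continues for at least 12 months after the last dose (Protocol 5.3.1), so the data will exist. Assumptions: 6 months is 26 weeks; rescue is spread evenly over Weeks 24 to 76; no withdrawal or clinical cut-off falls inside the window.

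Extra weeks = last infusion week + 26 − rescue week.

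- Rescue at Weeks 24–26 (2 weeks): 26 down to 24, mean 25
- Rescue at Weeks 26–50 (24 weeks): 26 down to 2, mean 14
- Rescue at Weeks 50–52 (2 weeks): 26 down to 24, mean 25
- Rescue at Weeks 52–76 (24 weeks): 26 down to 2, mean 14

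Mean = (2×25 + 24×14 + 2×25 + 24×14)/52 = 772/52 = 14.8 weeks.

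Time beyond Week 76 arises only after rescue at Weeks 52–76, when the window closes at Week 52 + 26 = Week 78. That is 2 weeks each, so 2×24/52 = 0.9 week on average, about 6% of 14.8. The rest lies within the period where SAP 4.5 applies one rule to both arms. The All Exposure tables start at first dose, however, so within them the whole 14.8 weeks differs by arm.

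For rescue during continued blinded treatment, with infusions 26 weeks apart from Week 80 and rescue falling evenly between them, the extra time is 0 to 26 weeks, mean 13.

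**3. Corticosteroid-only rescue under the literal reading**

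Take an obinutuzumab patient with such rescue at Weeks 64–76 who enters OLT at Week 80, with infusions at Weeks 80, 82, 104, 106 and 132. Lost time = min(cut-off week, 132 + 26) − rescue week.

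- Cut-off at Week 106: 106 − 76 = 30 to 106 − 64 = 42 weeks, covering 4 infusions
- Cut-off at Week 132: 56 to 68 weeks, covering 5 infusions
- OLT ends at OLT Week 52 and cut-off is at Week 158 or later: 82 to 94 weeks

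Now take a placebo patient with such rescue at Week 70 who starts OLT at Week 80. The obinutuzumab window would start at Week 80 and end at Week 70, so it is empty.

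**4. Illustration of the effect on events**

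None of these inputs is in the documents: 10 SAEs per 100 patient-years before rescue, 5–20% of the 126 planned placebo patients rescued at Weeks 24–76, and a post-rescue rate 0.5 to 3 times the pre-rescue rate. The mean window is 14.85/52 = 0.2855 year.

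Extra placebo SAEs = 126 × share × 0.2855 × 0.10 × multiplier:

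- low: 126 × 0.05 × 0.2855 × 0.10 × 0.5 = 0.1
- high: 126 × 0.20 × 0.2855 × 0.10 × 3 = 2.2

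For the rate ratio with no true difference, allow 1.5 years for a patient not rescued (to Week 78) and 0.96 year before rescue (to Week 50). At 20% rescued, pre-rescue time is 0.8×1.5 + 0.2×0.96 = 1.392 years per patient and post-rescue time is 0.2×0.2855 = 0.0571.

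- Multiplier 3: placebo rate = (13.92 + 1.71)/1.449 = 10.79, ratio 10/10.79 = 0.93
- Multiplier 0.5: placebo rate = (13.92 + 0.29)/1.449 = 9.80, ratio 10/9.80 = 1.02

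With a multiplier of 1 the rates do not differ.

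**The case against.** Five arguments can be made for leaving the text alone.

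- **The placebo list does respond to rescue.** This is true for one agent: the limit at the day before obinutuzumab catches rescue with obinutuzumab given outside the protocol. A reader might infer from the missing word that no rescue ever ends placebo data; the text does not support that. The limit does not reach the other rescue agents.
- **SAP 4.6.7 is introduced as additional to 4.5, so the 4.5 rule carries over.** This has some force for the corticosteroid exemption, because 4.5 holds the only rescue rule written for safety data and 4.2.1.1 is an efficacy section. The empty window in step 3 also conflicts with the statement in 4.6.7 that placebo patients who switch will contribute data. A reader might infer that the sponsor plans to discard on-treatment obinutuzumab data; the documents support only a missing qualifier that permits that reading. The argument does not rescue the asymmetry, because 4.5 is limited to Week 76, refers later data to 4.6.7, and 4.6.7 then sets its own lists.
- **Post-rescue outputs are already planned.** They are, in SAP 4.5, for the Week 76 period. SAP 4.6.7 has no such statement.
- **After Week 80, loss of response may lead to OLT rather than rescue.** In that case the existing rule ends the placebo window. The 13-week mean therefore applies only to patients who receive rescue instead, and their number is unknown.
- **The analysis is descriptive and not a clean randomised comparison.** It pools patients who cross over, by treatment received, and some limits must differ by arm. This stands and keeps the point small, but it does not explain a different rescue rule.

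It would also be wrong to count placebo time after corticosteroid-only rescue as surplus. Under a rule aligned with 4.5, that time is properly kept.

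**Conclusion.** The point holds and is minor. As written, SAP 4.6.7 counts events after non-corticosteroid rescue for placebo but not for obinutuzumab, except where the rescue agent is obinutuzumab itself. The extra placebo window is at most 26 weeks per rescued patient under the 26-week convention; the 14.8-week mean rests on evenly spread rescue.

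For counts the direction is certain: events can only be added to placebo. For rates, neither size nor direction can be settled. The documents give no rescue or post-rescue event rates, and SAP 4.6.7 does not say that rates will be produced. The illustrative range of 0.1 to 2.2 extra SAEs and a rate ratio of 0.93 to 1.02 is only as good as its assumptions, and it leaves out any loss after corticosteroid-only rescue.

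That corticosteroid loss is conditional. It arises only if the unqualified phrase is read with SAP 4.2.1.1, and the 30 to 94 week figures apply only then.

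A reader might go further and infer that follow-up is cut short or that the trial's main safety comparison is biased. Neither follows. Patients remain under follow-up after rescue, the Week 76 safety analysis uses one rule for all, and the primary efficacy analysis is untouched.

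**What to change.** Use one rescue cut-off for both arms in SAP 4.6.7, aligned with 4.5: receipt of rescue therapy, excluding corticosteroid-only rescue.

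- Add it to the placebo list and to the bullet for placebo patients with an adequate response.
- Add the corticosteroid exclusion to the obinutuzumab list. This also removes the empty window for placebo patients who switch, because the other forms of rescue bar OLT.
- Extend the limited post-rescue outputs already planned in SAP 4.5 to this analysis, for both arms.

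Removing the rescue cut from both arms would also restore symmetry, but it would depart from 4.5. The cost is SAP wording and reprogramming of one derived end date. No new data are needed and patient management does not change.

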4.7 INTERIM ANALYSES

No efficacy interim analyses are planned.

5. SUPPORTING DOCUMENTATION

This section is not applicable, since there is no additional supporting document.

Appendix 1 Changes to Protocol-Planned Analyses

The time points of the following exploratory endpoints have been updated following the schedule of assessment of the 24-hour UPCR as follows.

- Proportion of patients who achieve CRR at Weeks 24 and 50
- Proportion of patients who achieve proteinuric response at Weeks 24 and 50
- Proportion of patients who achieve ORR at Weeks 24 and 76

Week 36 has been replaced by Week 24 and Week 64 has been removed.

Appendix 2 Psychometric Validation of the FACIT-Fatigue Scale in LN Patients: Analysis Plan

BACKGROUND

Patients with lupus nephritis (LN) experience significant symptoms due to their disease that impact their daily lives. Of the identified core symptoms of LN, fatigue is one of the most prevalent and bothersome to patients (Williams-Hall et al. 2022; Raymond et al. 2021; Eudy et al. 2022; Gallop et al. 2012; Mathias et al. 2018). In studies of patients with active proliferative LN, more than 90% of patients reported experiencing fatigue at a baseline evaluation (Daleboudt et al. 2011; Grootscholten et al. 2007; Arends et al. 2014). Furthermore, in these patients fatigue was generally reported as their most bothersome symptom. The frequency of fatigue has been shown to be similar between patients with and without active LN (Bland et al. 2018). Due to the importance of fatigue in the LN patient experience and the clinical and patient-reported significance of the symptom, it was deemed important to assess the effect of obinutuzumab on fatigue symptoms in LN in the Phase III REGENCY trial. In this study, fatigue was assessed using the FACIT-Fatigue scale. The associated key secondary endpoint is mean change from Baseline at Week 76.

This analysis plan has been developed to provide psychometric validation for the use of the FACIT-fatigue scale in LN patients in order to facilitate USPI inclusion.

OBJECTIVE

 To establish the reliability, validity, and responsiveness of the FACIT-Fatigue scale in LN patients to facilitate potential label inclusion..

The FACIT-Fatigue is presented in Table 1. The FACIT-Fatigue is one of many different FACIT scales that are part of a collection of health-related quality of life (HRQOL) questionnaires targeted to the management of chronic illness and referred to as The FACIT Measurement System (Webster et al. 2003). The FACIT-Fatigue is a 13-item measure that assesses self-reported fatigue and its impact upon daily activities and function (Tennant 2015).

Table 1 FACIT-Fatigue Scale (Version 4)

Health Concept	FACIT Item	Question	Response Options
Fatigue	HI7	I feel fatigued	0 = Not at all 1 = A little bit
	HI12	I feel weak all over	
	An1	I feel listless ("washed out")	
	An2	I feel tired	
Daily / Role Functioning	An3	I have trouble starting things because	
		I am tired	
	An4	I have trouble finishing things	
		because I am tired	
Physical Functioning	An5	I have energy	2 = Somewhat
Daily / Role Functioning	An7	I am able to do my usual activities	3 = Quite a bit 4 = Very Much
	An8	I need to sleep during the day	
	An12	I am too tired to eat	
	An14	I need help doing my usual activities	
	An15	I am frustrated by being too tired to	
		do the things I want to do	
Social Functioining	An16	I have to limit my social activity	-
		because I am tired	

FACIT-FATIGUE RESPONSE OPTIONS

All 13 items of the FACIT-Fatigue are measured on a Likert scale with 5 response options and range from 0 (Not at all) to 4 (Very Much).

FACIT-FATIGUE SCORING

To score the FACIT-Fatigue, reversals are first performed for the scores on two items (An5 and An7) then all individual items are summed to obtain a score. The sum of the item scores is multiplied by the number of items in the subscale, then divided by the number of items answered. This produces the final score which ranges from 0 to 52. Higher scores indicate less fatigue (Yellen et al.1997).

FACIT-FATIGUE RECALL PERIOD

The recall period of the FACIT-Fatigue is the past 7 days.

DATA

All data will stem from a single pivotal Phase III trial, REGENCY.

ANALYSES TO SUPPORT THE OBJECTIVE

RELIABILITY

Internal consistency - Internal consistency is an estimate of reliability based on the average correlation between items in a scale. This is represented by calculating Cronbach's alpha.

Calculate Cronbach's alpha using data from the 13 scale items in relation to the total FACIT-Fatigue scale score at Baseline. Cronbac's alpha ≥0.7 suggests reasonable internal consistency. In addition, estimates of lambda 2, 4, and omega will be calculated for comparison.

Test-retest reliability - Calculate two-way, mixed effects ICC between FACIT-Fatigue scores derived at Baseline and Week 24. Correlations ≥0.7 indicate reasonable test-retest reliability.

VALIDITY

Construct validity - assesses the degree to which a scale actually measures the construct it was designed to measure. Two estimates of construct validity will be used - convergent validity and discriminant validity.

Convergent validity - Tests if a scale is correlated with other scales that measure the same or related construct. Calculate Spearman's correlation coefficient and Weighted Kappa between:

- FACIT-Fatigue score and SF-36 Vitality, Physical Functioning, Bodily Pain, Role Physical, and General Health domain scores derived at Baseline
- FACIT-Fatigue score and SF-36 Physical Component Summary (PCS) score derived at Baseline

Discriminant validity - Tests if a scale is independent from other scales that measure constructs that differ from the one being considered. Calculate Spearman's correlation coefficient and Weighted Kappa between:

- FACIT-Fatigue score and SF-36 Mental Health, Role Emotional, and Social Functioning domain scores derived at Baseline
- FACIT-Fatigue score and SF-36 Mental Component Summary (MCS) score derived at Baseline

Known groups validity - Tests if a scale can differentiate between groups known to differ in terms of a disease category. Patients will be grouped according to the British Isles of Lupus Assessment Group (BILAG) General domain and BILAG Musculoskeletal domain scores (A, B, or C/D/E). ANOVA will be used to test the mean differences in FACIT-Fatigue scores between groups. Effect sizes (mean difference/SD) will be calculated for the differences between adjacent groups. A second analysis will be conducted using patient groups based on differing scores for Safety of Estrogens in Lupus Erythematosus National Assessment-Systemic Lupus Erythematosus Disease Activity Index (SELENA-SLEDAI), a measure of reduction in global disease activity. Two groups will be formed: a high SELENA-SLEDAI score group (indicating more active disease - SELENA-SLEDAI score ≥10); and a low SELENA-SLEDAI score group (SELENA-SLEDAI <6). Both analyses will be based on Week 76 data.

Content Validity - This form of validity is typically established using qualitative interviews with patients, and sometimes physicians, to determine if a scale's content maps well with the patient's perspective of their disease burden. There is reasonable evidence for content validity in SLE/LN that will be culled from the existing literature.

RESPONSIVENESS OF FACIT-FATIGUE TO CHANGES IN DISEASE ACTIVITY

In this section, the responsiveness of the FACIT-Fatigue score in relation to changes in disease status is assessed. For this analysis, the extent to which important longitudinal changes in Physician's Global Assessment (PGA), Subject's Global Assessment (SGA), and BILAG grade are associated with changes in the FACIT-Fatigue score will be examined. PGA and SGA score changes will be classified as better, worse, or unchanged, with a 30% increase or decrease used as the criterion for classifying meaningful change. BILAG grade change between consecutive assessments will be categorized as more active, stable, or less active. Moving from a BILAG score of D/E to C or vice versa will be classified as stable since those changes are not considered clinically meaningful. ANOVA will be used to compare mean FACIT-Fatigue score change between groups. Both analyses will be based on Week 76 data.

DERIVATION OF MINIMUM CLINICALLY IMPORTANT DIFFERENCE (MCID) - A RESPONDER THRESHOLD FOR ASSESSING WITHIN-PATIENT IMPROVEMENT

In order to derive an MCID for the FACIT-Fatigue scale, the SF-36 Vitality Domain as an anchor will be employed. The Vitality domain has the advantage of assessing a similar construct to the FACIT-Fatigue scale and is built from fairly well-delineated categorical response choices ("all of the time"=1; 'most of the time"=2; "a good bit of the time"=3; "some of the time"=4; "a little of the time"=5; and "none of the time"=6). For this analysis, an SF-36 Vitality domain responder will be defined as a patient who satisfies the following:

How much of the time during the past 7 days...

VT1 - did you feel full of pep? (must score a 3 or less);

VT2 - did you have a lot of energy? (must score 3 or less);

VT3 - did you feel worn out? (must score 4 or higher);

VT4 - did you feel tired? (must score 4 or higher)

The mean improvement in FACIT-Fatigue score (rounded up to the nearest integer) for the subpopulation of SF-36 VT responders between Baseline and Week 76 will serve as the estimated MCID for the FACIT-Fatigue scale. The proportion of subjects from each treatment group who have improved by the MCID value or greater between Baseline and Week 76 will be calculated. A chi-square test will be conducted to evaluate the differences

REFERENCES

